2.2 Analysis sets

[figure not shown]
The following analysis sets will be used in this study:

Randomized set: The randomized set will be defined as all participants who were randomized. Unless otherwise specified, mis-randomized participants (mis-randomized in IRT) will be excluded from the randomized set.

Mis-randomized participants are defined as those participants who were mistakenly randomized into the IRT prior to the site confirming all eligibility criteria had been met and to whom no study medication was given. Mis-randomized participants are treated as screen failures.

Full analysis set (FAS): The FAS will be comprised of all participants from the randomized set to whom study treatment has been assigned. Following the intent-to-treat principle, participants will be evaluated according to the treatment assigned to at randomization.

Three subsets of FAS are defined as follows:

- Psoriasis subset: The psoriasis subset will include all FAS participants who have $\geq 3\%$ of the BSA affected by psoriatic skin involvement at BSL.

Safety set: The safety set includes all participants who took at least one dose of study treatment during the treatment period. Participants will be evaluated according to treatment received.

2.2.1 Subgroup of interest

Not applicable.

2.3 Patient disposition, demographics and other baseline characteristics

Summary statistics will be presented for continuous demographic and BSL characteristic variables for each treatment sequence and for all participants in the randomized set. The number and percentage of participants in each category will be presented for categorical variables for each treatment group and all participants.

The following demographic variables and BSL disease characteristics, if collected, will be analyzed:

Continuous variables:

- Age
- Height
- Weight
- Body mass index (BMI) = (body weight in kilograms) / (height in meters)²

Categorical variables:

- Age categories (<65 years, 65-74, 75 years and older)
- Gender
- Race
- Ethnicity
- Smoking status at baseline

The following disease specific baseline characteristics and history of disease will be summarized.

- Anti-TNF treatment history (naïve or inadequate responder), ACR components and other disease-related measures (e.g., DAS28, presense of dactylitis, presense of enthesitis, time

since first diagnosis of PsA, participant with psoriasis $\geq 3\%$), etc., number of prior biologic PsA therapies, dose of MTX or other DMARD at randomization.

Medical history

A history of PsA with focus on previous extra-articular involvement and past therapies for PsA will be obtained and summarized by treatment group for all patients in the Randomized set. Any other significant prior or active medical condition at the time of signing informed consent will be recorded and coded using the MedDRA dictionary. These medical conditions will be summarized by primary system organ class and preferred term.

Data on baseline and demographic characteristics will be summarized by treatment sequence at Final Analysis.

2.3.1 Patient disposition

The number of participants screened and the reasons for screen failures were presented in the previous primary endpoint analysis thus will not be repeated. The number and percentage of participants in the randomized set who completed the study periods and who discontinued from treatment or study prematurely (including the reason for discontinuation) will be presented at the end of each treatment period (e.g., Week 52 and entire treatment period), if appropriate, for each treatment sequence and all participants.

For each protocol deviation (PD), the number and percentage of participants for whom the PD applied will be tabulated by treatment sequence on the randomized set.

2.4 Treatments (study treatment, rescue medication, concomitant therapies, compliance)

2.4.1 Study treatment / compliance

The analysis of study treatment data will be based on the safety set. The number of visits with active and placebo injections received will be presented by treatment group.

The duration of exposure to study treatment will also be summarized by treatment group. In addition, the number and percentage of participants with cumulative exposure levels (e.g. any exposure, ≥ 1 week, ≥ 2 weeks, ≥ 3 weeks, ≥ 4 weeks, ≥ 8 weeks, etc.) will be presented.

Duration of exposure is defined as the time from first dose of study treatment to the time of treatment switch (for participants who switch treatment) or minimum of (last dose of the treatment + 84 days) and (last visit date). Participants who switch treatment during the study (e.g., from placebo to active treatment) will have exposure to both medications/doses using the appropriate start and stop dates.

Duration of exposure (years) = duration of exposure (days) / 365.25

Duration of exposure (100 subject years) = duration of exposure (years) / 100

The analysis of duration of exposure described above will be done for the entire study treatment period by treatment group.

2.4.2 Prior, concomitant and post therapies

Prior and concomitant treatments will be summarized in separate tables by treatment group for the safety set.

Prior medications are defined as treatments taken and stopped prior to first dose of study treatment. Any medication given at least once between the day of first dose of randomized study treatment and the date of the last study visit will be a concomitant medication, including those which were started pre-BSL and continued into the period where study treatment is administered.

Medications will be presented in alphabetical order, by Anatomical Therapeutic Classification (ATC) codes and grouped by anatomical main group. Tables will show the overall number and percentage of participants receiving at least one treatment of a particular ATC code and at least one treatment in a particular anatomical main group.

Significant prior and concomitant non-drug therapies and procedures will be summarized by primary system organ class and WHODrug preferred term.

Prior surgeries and procedures are defined as surgeries and procedures done prior to first dose of study treatment. Any surgeries and procedures done between the day of first dose of study treatment and within the date of the last study visit will be a concomitant surgeries and procedures, including those which were started pre-BSL and continued into the period where study treatment is administered.

The number and percentage of participants receiving prior and concomitant PsA therapy will be presented by randomized treatment group as well as the reasons for stopping their therapies (primary lack of efficacy, secondary lack of efficacy, lack of tolerability, other) and the total duration of exposure to PsA therapies previously. NSAID, glucocorticoid and DMARD (MTX, Leflunomide, Sulfasalazine) use will be summarized.

Prior therapies have been summarized at Primary endpoint analysis; therefore, no summary tables or listings will be reproduced at the Final Analysis.

2.5 Analysis of the primary objective

The primary objective of this study is to assess the efficacy of secukinumab relative to placebo at week 16 based on the proportion of participants achieving an ACR20 response. The consistency of the treatment difference between this bridging study and the pooled efficacy data of global pivotal studies (CAIN457F2312, CAIN457F2318, CAIN457F2336 and CAIN457F2342) were evaluated at the Primary endpoint analysis and will not be repeated at the Final Analysis.

2.5.1 Primary endpoint

The primary efficacy variable was ACR20 response at Week 16. The analysis of the primary efficacy variable was based on the FAS. Primarily, CRP will be used instead of ESR to calculate ACR response; ESR will only be used in the event CRP is missing.

The clinical question of interest is: What is the effect of secukinumab 150 mg s.c. versus placebo on the composite endpoint ACR20 response at Week 16 and the completion of 16 week-treatment in Chinese patients with active PsA?

The primary estimand is described by the following attributes:

- a. Population: defined through appropriate inclusion/exclusion criteria to reflect the targeted PsA population
- b. Variable: composite of remaining on the study and on randomized treatment through 16 weeks and achieving ACR20 response at 16 weeks
- c. Treatment of interest: Secukinumab 150 mg s.c. and Placebo
- d. Intercurrent event: the intercurrent event of discontinuation from treatment or study prior to Week 16 has been addressed via the composite variable definition
- e. Population-level summary: difference in proportions of responders between secukinumab and placebo groups

The estimand of binary variables is (s.c. secukinumab regimen vs placebo) obtained from a logistic regression model with treatment as a factor and weight as a covariate at week 16 in the FAS population. Difference in marginal response proportions were computed for s.c. secukinumab regimen and placebo regimen utilizing the logistic regression model fitted. In the analysis subjects discontinued study drug, dropping out or being unblinded before week 16 or having missing response data at week 16 are considered as non-responders.

2.5.2 Statistical hypothesis, model, and method of analysis

The statistical hypothesis, model and method of analysis have been presented in the SAP for Primary endpoint analysis and will not be repeated in this document.

2.5.3 Handling of missing values/censoring/discontinuations

The handling of missing values has been presented in the SAP for Primary endpoint analysis and will not be repeated in this document.

2.5.4 Supportive analyses

The supportive analyses have been presented in the SAP for Primary endpoint analysis and will not be repeated in this document.

2.6 Analysis of the secondary objectives

2.6.1 Secondary endpoints

The secondary efficacy variables are described below. Secondary efficacy variables were analyzed using the FAS population. Handling of missing data for secondary variables were the same as for the primary variable.

- ACR50 response rate at Week 16

- Change from baseline in DAS28-CRP at Week16
- Change from baseline in PASDAS at Week 16
- Change from baseline in SF36-PCS at Week 16
- Change from baseline in HAQ-DI[©] at Week 16

The clinical questions of interest are:

- What is the effect of secukinumab 150 mg s.c. versus placebo on the composite endpoint ACR50 response at week 16 and the completion of 16 week-treatment in Chinese patients with active PsA?
- What is the effect of secukinumab 150 mg s.c. versus placebo on change from BSL in DAS28-CRP at week 16 in Chinese patients with active PsA had patients completed 16 week-treatment?
- What is the effect of secukinumab 150 mg s.c. versus placebo on change from BSL in PASDAS at week 16 in Chinese patients with active PsA had patients completed 16 week-treatment?
- What is the effect of secukinumab 150 mg s.c. versus placebo on change from BSL in SF-36 PCS at week 16 in Chinese patients with active PsA had patients completed 16 week-treatment?
- What is the effect of secukinumab 150 mg s.c. versus placebo on change from BSL in HAQ-DI at week 16 in Chinese patients with active PsA had patients completed 16 week-treatment?

The justification for targeting the treatment effect is that we wish to estimate the effect of the study drug for the full duration when administered without dose changes.

The estimand definition of all secondary objectives related to response (e.g., ACR50, etc.) will have the same attributes as that for the primary estimand, except for the variable of interest.

Estimand definition for the secondary continuous variables (e.g., HAQ-DI[©], etc.) is the following:

- a. Population: defined through appropriate inclusion/exclusion criteria to reflect the targeted PsA population
- b. Variable: change from baseline in the variable of interest
- c. Treatment of interest: Secukinumab 150 mg s.c. and Placebo
- d. Intercurrent event: discontinuation from treatment or study prior to Week 16
- e. Population-level summary: difference in variable means between secukinumab and placebo groups

2.6.2 Statistical hypothesis, model, and method of analysis

The statistical hypothesis, model and method of analysis have been presented in the SAP for Primary endpoint analysis and will not be repeated in this document.

2.6.3 Handling of missing values/censoring/discontinuations

The statistical hypothesis, model and method of analysis have been presented in the SAP for Primary endpoint analysis and will not be repeated in this document.

2.7 Safety analyses

Summaries will be performed for the entire treatment period on the Safety Set.

Safety analysis will be performed on treatment received or actual treatment as described below:

The actual treatment or treatment received for summaries of safety data would differ to the treatment assigned at randomization only if a subject received the wrong treatment during the entire study.

For those subjects who received not the treatment assigned at randomization, i.e., who received erroneously the wrong treatment at least once, an additional AE listing will be prepared displaying which events occurred after the treatment errors.

Subjects who switch treatment during the study (e.g. from placebo to active treatment) will be counted to both groups using the appropriate start and stop exposure date.

The safety variables to be analyzed include Adverse events (AEs)/Serious Adverse Events (SAEs), clinical laboratory tests (hematology, chemistry and urinalysis), physical examination results, ECGs, vital signs and deaths. Safety variables are to be tabulated by descriptive statistics (n, mean, median, standard deviation, minimum, and maximum; or n and percent). No formal statistical testing is planned.

2.7.1 Adverse events (AEs)

Treatment-emergent adverse events (i.e., events started after the first dose of study treatment or events present prior to the first dose of study treatment but increased in severity based on preferred term and on or before last dose + 84 days) will be summarized.

Adverse events will be summarized by presenting, for each treatment group, the number and percentage of participants having any AE, having an AE in each primary system organ class and having each individual AE (preferred term). Summaries will also be presented for AEs by severity and for study treatment related AEs. If a participant reported more than one adverse event with the same preferred term, the adverse event with the greatest severity will be presented. If a participant reported more than one adverse event within the same primary system organ class, the participant will be counted only once with the greatest severity at the system organ class level, where applicable. Serious adverse events will also be summarized.

These summaries may be presented separately by placebo controlled period and entire study.

As appropriate, the incidence of AEs will be presented per 100 patient years of exposure (exposure-adjusted incidence rates).

Separate summaries will be provided for death, serious adverse event, other significant adverse events leading to discontinuation and adverse events leading to dose adjustment (including study treatment discontinuation).

A graphical display of relative frequencies within system organ classes and relative risks, as appropriate, will be presented.

Adverse events will also be reported separately by Standardized MedDRA Query (SMQ) according to MedDRA. The MedDRA version used for reporting the study will be described in a footnote.

Treatment emergent and non-treatment emergent adverse events will be listed.

Algorithms for date imputations will be provided in Programming Datasets Specifications.

For serious adverse events (SAEs) occurred during screening a listing were prepared for all subjects screened including screening failures at the primary endpoint analysis.

The safety analysis that will be performed for treatment emergent AEs and on treatment labs and vital signs for each analysis period is described in Table 2-1.

The data in the period of Day 1 – Week 16 were presented at the primary endpoint analysis; the data in the period of Entire treatment will be presented at the Final Analysis.

Table 2-1 Overview of analysis on some safety endpoints

Analysis period	AEs & SAEs	AEs-SMQ	AEs by severity	study drug related AEs	notables for (vitals/ECG), lab criteria	Risk
Day 1 – Week 16	• crude incidence	• crude incidence	• crude incidence	• crude incidence	• crude incidence	• crude incidence
Entire Treatment	• crude incidence • exp.time adjusted incidence	• exp.time adjusted incidence	• crude incidence	• crude incidence	• crude incidence	• crude incidence • exp.time adjusted incidence

* Exposure-adjusted incidence rates will be done for the following:
At the PSOC for AE and SAE and Level 1 for Risks and SMQ analysis

For the legal requirements of ClinicalTrials.gov and EudraCT, two required tables on treatment emergent adverse events which are not serious adverse events with an incidence greater than 2% and on treatment emergent serious adverse events and SAE suspected to be related to study treatment will be provided by system organ class and preferred term on the safety set population.

If for a same patient, several consecutive AEs (irrespective of study treatment causality, seriousness and severity) occurred with the same SOC and PT:

- a single occurrence will be counted if there is ≤ 1 day gap between the end date of the preceding AE and the start date of the consecutive AE
- more than one occurrence will be counted if there is > 1 day gap between the end date of the preceding AE and the start date of the consecutive AE

For occurrence, the presence of at least one SAE / SAE suspected to be related to study treatment / non SAE has to be checked in a block e.g., among AE's in a ≤ 1 day gap block, if at least one SAE is occurring, then one occurrence is calculated for that SAE.

The number of deaths resulting from SAEs suspected to be related to study treatment and SAEs irrespective of study treatment relationship will be provided by SOC and PT.

2.7.1.1 Adverse events of special interest / grouping of AEs

Safety topics of interest, such as risks defined in the Safety Profiling Plan (SPP), Risk Management Plan (RMP) or topics of interest regarding signal detection or routine analysis are defined in the Program Case Retrieval Sheet.

Number and percentage of subjects with an event for SPP/RMP risks will be summarized.

2.7.2 Deaths

Separate summaries will be provided for deaths.

2.7.3 Laboratory data

The summary of lab data will only include on treatment data, which are defined as those lab assessments after the first dose of study treatment and on or before last dose +84 days.

The summary of laboratory evaluations will be presented for three groups of laboratory tests (hematology, serum chemistry and urinalysis).

For urinalysis, frequency tables will be presented. Specifically, the urine specific gravity will be presented in the following categories: <1.001, 1.001-1.005, 1.006-1.010, 1.011-1.015, 1.016-1.020, 1.021-1.025, 1.026-1.030, 1.031-1.035, >1.035. Descriptive summary statistics for the change from BSL to each study visit will be presented. These descriptive summaries will be presented by test group, laboratory test and treatment group. Change from BSL will only be summarized for participants with both BSL and post BSL.

For each parameter, the maximum change from BSL within each study period will be evaluated analogously.

In addition, shift tables will be provided for all parameters to compare a participant's BSL laboratory evaluation relative to the visit's observed value. For the shift tables, the normal laboratory ranges will be used to evaluate whether a particular laboratory test value was normal, low, or high for each visit value relative to whether the BSL value was normal, low, or high. These summaries will be presented by laboratory test and treatment group. Shifts will be presented as well as for most extreme values post-BSL.

The following laboratory parameters will be analyzed with respect to numerical Common Terminology Criteria for Adverse Events (CTCAE) grades, given in hemoglobin, platelets, white blood cell count, neutrophils, lymphocytes, creatinine, total bilirubin (TBL), gamma-glutamyl transferase (GGT), alanine aminotransferase (ALT), aspartate aminotransferase (AST), alkaline phosphatase (ALP), glucose, cholesterol, triglycerides (TG). These summaries will be split into hematology and chemistry.

Table 2-2 CTCAE grades for laboratory parameters to be analyzed

CTCAE v4.0 Term	Grade 1	Grade 2	Grade 3	Grade 4
HGB decreased (Anemia)	<LLN - 100 g/L	<100 - 80 g/L	<80 g/L	Life-threatening consequences; urgent intervention
Platelet count decreased	<LLN - 75.0 x10e9 /L	<75.0 - 50.0 x10e9 /L	<50.0 - 25.0 x10e9 /L	<25.0 x 10e9 /L
White blood cell decreased	<LLN - 3.0 x 10e9 /L	<3.0 - 2.0 x 10e9 /L	<2.0 - 1.0 x 10e9 /L	<1.0 x 10e9 /L
Neutrophil count decreased	<LLN - 1.5 x 10e9 /L	<1.5 - 1.0 x 10e9 /L	<1.0 - 0.5 x 10e9 /L	<0.5 x 10e9 /L
Lymphocyte count decreased	<LLN - 0.8 x 10e9/L	<0.8 - 0.5 x 10e9 /L	<0.5 - 0.2 x 10e9 /L	<0.2 x 10e9 /L
Creatinine increased*	>1 - 1.5 x baseline; >ULN - 1.5 x ULN	>1.5 - 3.0 x baseline; >1.5 - 3.0 x ULN	>3.0 baseline; >3.0 - 6.0 x ULN	>6.0 x ULN
TBL increased	>ULN - 1.5 x ULN	>1.5 - 3.0 x ULN	>3.0 - 10.0 x ULN	>10.0 x ULN
GGT increased	>ULN - 2.5 x ULN	>2.5 - 5.0 x ULN	>5.0 - 20.0 x ULN	>20.0 x ULN
ALT increased	>ULN - 3.0 x ULN	>3.0 - 5.0 x ULN	>5.0 - 20.0 x ULN	>20.0 x ULN
AST increased	>ULN - 3.0 x ULN	>3.0 - 5.0 x ULN	>5.0 - 20.0 x ULN	>20.0 x ULN
ALP increased	>ULN - 2.5 x ULN	>2.5 - 5.0 x ULN	>5.0 - 20.0 x ULN	>20.0 x ULN
Glucose increased (Hyperglycemia)	>ULN - 8.9 mmol/L	>8.9 - 13.9 mmol/L	>13.9 - 27.8 mmol/L	>27.8 mmol/L
Glucose decreased (Hypoglycemia)	<LLN - 3.0 mmol/L	<3.0 - 2.2 mmol/L >7.75 - 10.34 mmol/L	<2.2 - 1.7 mmol/L >10.34 - 12.92 mmol/L	<1.7 mmol/L
Cholesterol high	>ULN - 7.75 mmol/L			>12.92 mmol/L
Hypertriglyceridemia	1.71 - 3.42 mmol/L	>3.42 - 5.7mmol/L	>5.7 - 11.4 mmol/L	>11.4 mmol/L

* Note: for "creatinine increased" the baseline criteria do not apply

Shift tables will be presented comparing baseline laboratory result (CTCAE grade) with the worst results (expressed in CTCAE grade) during the treatment phase (either initial up to week 16 or entire) analyzed. Of note, baseline will be defined as last assessment prior to first dosing in initial treatment phase.

Summaries for newly occurring or worsening clinically notable lipid abnormalities will also be provided cumulatively for each of the following parameters and categories:

- HDL:
 - <=LLN
 - <0.8x LLN
- LDL, cholesterol, triglycerides:
 - >=UNL
 - >1.5 x ULN

- > 2.5 x ULN

Newly occurring or worsening liver enzyme abnormalities will also be summarized based on the event criteria given in Table 2-3:

Table 2-3 Liver-related events

Parameter	Criterion
ALT	>3xULN; >5xULN; >8xULN; >10xULN, >20xULN
AST	>3xULN; >5xULN; >8xULN >10xULN; >20xULN
ALT or AST	>3xULN; >5xULN; >8xULN >10xULN; >20xULN
TBL	>1.5xULN; >2xULN; >3xULN
ALP	>2xULN; >3xULN; >5xULN
ALT or AST & TBL	ALT or AST >3xULN & TBL >2xULN; ALT or AST >5xULN & TBL >2xULN; ALT or AST >8xULN & TBL >2xULN; ALT or AST >10xULN & TBL >2xULN;
ALP & TBL	ALP >3xULN & TBL >2xULN ALP >5xULN & TBL >2xULN
ALT or AST & TBL & ALP	ALT or AST >3xULN & TBL >2xULN & ALP <2xULN (Potential Hy's Law) Note: elevated ALP may suggest obstruction as a consequence of gall bladder or bile duct disease; ALP may also be increased in malignancy. FDA therefore terms Hy's Law cases as indicators of pure hepatocellular injury. This does not mean that cases of ALT or AST >3xULN & TBL >2xULN & ALP \geq 2xULN may not result in severe DILI.

Notes:

1) In studies which enroll subjects with pre-existing liver disease, baseline LFT may be increased above ULN; in such a case it is meaningful to add the condition "and worse than baseline" to the abnormality criteria

For a combined criterion to be fulfilled, all conditions have to be fulfilled on the same visit. The criteria are not mutually exclusive, e.g., a subject with ALT = 6.42xULN is counted for ALT > 3xULN and ALT > 5x ULN.

Individual subject data listing may be provided for subjects with abnormal laboratory data. Data of subjects with newly occurring or worsening liver enzyme abnormalities may be listed in an additional listing.

The laboratory values below Lower Level of Quantification (LLQ) or above Upper Level of Quantification (ULQ) will be imputed as LLQ or ULQ, respectively. The numerical part of the reported result will be treated as the actual LLQ or ULQ.

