| Visit Name | -10 to -4 | ≤-4 to BSL | Base line | Wk 1 | Wk 2 | Wk 3 | Wk 4 | Wk 8 | Wk 12 | Wk16/ End of TP1/TD ² | Wk 20 | Wk 24 | Wk 28 | Wk 32 | Wk 36 | Wk 40 | Wk 44 | Wk 48 | Wk52/ End of TP2/TD ² | F60 (End of study/PSW) ² |
| Weeks | -10 to -4 | -4 to 0 | 0 | 1 | 2 | 3 | 4 | 8 | 12 | 16 | 20 | 24 | 28 | 32 | 36 | 40 | 44 | 48 | 52 | 60 |
| Days | -70 to -28 | -28 to 0 | 1 | 7 | 14 | 21 | 28 | 56 | 84 | 112 | 140 | 168 | 196 | 224 | 252 | 280 | 308 | 336 | 364 | 420 |
| Prior/Concomi tant medication/ Non-drug therapy | х | x | х | x | × | x | x | x | x | х | x | x | x | x | х | x | x | x | x | Х |
| Pregnancy (Serum) ^{4,6} | | S | | | | | | | | | | | | | | | | | | S |
| Pregnancy Test ^{4,6,9} | | | S | | | | S | | s | S | | S | | S | | s | | | S | S |
| Adverse Events/SAE (incl. injection site reaction & occurrence of injections) ¹⁰ | х | х | х | x | х | x | x | x | x | х | x | х | x | x | x | x | x | x | x | Х |
| ANA | | | Х | | | | | | | Х | | | | | | | | | Х | |
| anti-double stranded DNA antibodies (anti-dsDNA) | | | х | | | | | | | х | | | | | | | | | х | |
| Anti-CCP | Х | | | | | | | | | | | | | | | | | | | |
| Rheumatoid factor (RF) | х | | | | | | | | | | | | | | | | | | | |
| Hematology | | Х | Х | | | | | | Х | Х | | | Х | | | Х | | | Х | Х |
| Blood chemistry | | х | х | | | | | | х | х | | | х | | | x | | | х | х |

Confidential

Page **48** of **106** Protocol No. CAIN457F2367

| Period | Scree | ening ¹ | | т | reatm | ent P | eriod | 1 (TP | 1) | | | | Т | reatm | ent Per | iod 2 | (TP2) | | | Post-Treatment Follow-Up |
|--|---------------|--------------------|--------------|---------|---------|---------|---------|---------|----------|--|----------|----------|----------|----------|----------|----------|----------|----------|--|-------------------------------------|
| Visit Name | -10 to -4 | ≤-4 to BSL | Base line | Wk 1 | Wk 2 | Wk 3 | Wk 4 | Wk 8 | Wk 12 | Wk16/ End of TP1/TD ² | Wk 20 | Wk 24 | Wk 28 | Wk 32 | Wk 36 | Wk 40 | Wk 44 | Wk 48 | Wk52/ End of TP2/TD ² | F60 (End of study/PSW) ² |
| Weeks | -10 to -4 | -4 to 0 | 0 | 1 | 2 | 3 | 4 | 8 | 12 | 16 | 20 | 24 | 28 | 32 | 36 | 40 | 44 | 48 | 52 | 60 |
| Days | -70 to -28 | -28 to 0 | 1 | 7 | 14 | 21 | 28 | 56 | 84 | 112 | 140 | 168 | 196 | 224 | 252 | 280 | 308 | 336 | 364 | 420 |
| Urinalysis | | Х | Х | | | | | | Х | Х | | | Х | | | Х | | | Х | Х |

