¹² BSA evaluation at BSL to determine if should be done or not.

¹³ Sample has to be obtained fasting.

¹⁴ Optional

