8.4.1 Laboratory evaluations

A central laboratory will be used for analysis of all specimens listed below (except for ESR, pregnancy test, Hepatitis B Virus (HBV), Hepatitis B Virus (HCV) and Human immunodeficiency virus (HIV). Details on the collection, shipment of samples and reporting of results by the central laboratory are provided in the laboratory manual. Refer to the Laboratory Manual for identification of laboratory reference range values and the schema for notification of site staff and Novartis for out of range values.

Blood withdrawals and safety assessments should be done prior to study treatment administration and should be taken as shown in Table 8-1.

Laboratory evaluations listed below are to be measured at scheduled visit as indicated in Table 8-1.

| Test Category | Test Name |
|---|--|
| Hematology | Hemoglobin, Red blood cells (RBC), Platelets, White blood cells, Differential (Basophils, Eosinophils, Lymphocytes, Monocytes, Neutrophils including Bands). |
| Chemistry | Albumin (Alb), Alkaline phosphatase (ALP), Alanine Aminotransferase (ALT), Aspartate Aminotransferase (AST), Gamma-glutamyl-transferase (GGT), Lactate dehydrogenase (LDH), Bicarbonate, Calcium, Magnesium, Phosphorus, Chloride, Sodium, Potassium, Creatinine, , Total Bilirubin, Total Protein, Blood Urea Nitrogen (BUN) or Urea, Uric Acid and Glucose. |
| Urinalysis | Macroscopic Panel: pH, Glucose, Protein, Blood, Bilirubin, Urobilinogen, Ketones, , Specific Gravity, White Blood Cells (WBC). A midstream urine sample (approx. 30 mL) will be obtained, in order to avoid contamination with epithelial cells and sediments, and allow proper assessments. Urine sample should be collected and sent to central lab for analysis. If the results are not in the normal ranges, the investigator will evaluate whether further testing is required or not. This testing will be done at the local lab. |
| Lipid panel | High-density Lipoprotein (HDL), Low-density Lipoprotein (LDL), total cholesterol and triglycerides. The lipid panel will be measured from a fasting sample. |
| Autoantibodies | Anti-nuclear antibodies (ANA) and anti-dsDNA will be assessed at the visits/time points indicated in Table 8-1. In addition, RF and anti-CCP must be tested negative for a participant being eligible in this study as per inclusion criteria 5. |

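### Glucose at Weeks 12, 28 and 40 carries no fasting requirement, so the baseline-to-worst glucose shift and maximum change in SAP 2.7.3 can be inflated, mostly at Grade 1

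*SAP*

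**What the plan says.** **Sampling.** Protocol Table 8-5 (Section 8.4.1) ends its chemistry list with "Blood Urea Nitrogen (BUN) or Urea, Uric Acid and Glucose" and attaches no fasting condition. For lipids the same table says "The lipid panel will be measured from a fasting sample". Footnote 13 of Table 8-1, attached to the lipids row only, says "Sample has to be obtained fasting".

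**Analysis.** SAP 2.7.3 names glucose among the parameters graded by CTCAE, and Table 2-2 starts hyperglycaemia Grade 1 just above the upper limit of normal, with no fasting qualifier. The graded analysis is described as "Shift tables will be presented comparing baseline laboratory result (CTCAE grade) with the worst results", taken over the initial period to Week 16 or over the entire period. For this table, "baseline will be defined as last assessment prior to first dosing in initial treatment phase". The section also says "For each parameter, the maximum change from BSL within each study period will be evaluated analogously", and it plans change from baseline by visit. Laboratory values count as on treatment up to 84 days after the last dose.

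**The concern.** A worst-value rule picks the highest of several draws. If the baseline comes from a visit that requires fasting and half of the later draws do not, a fed value is a likely candidate for the worst. The table would then show a move from normal to Grade 1 that reflects breakfast and not drug. The same applies to the maximum change, and the by-visit means could rise and fall with the fasting schedule. With no fasting status collected, the artefact could not be separated out afterwards.

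At stake is the reading of the descriptive glucose tables in the final analysis. The entire-treatment period reported there contains all three unrestricted draws.

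**Working it through.** **Step 1: visits, from Table 8-1.**

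| Row | Scheduled at |
|---|---|
| Blood chemistry (includes glucose) | Screening 2, baseline, Weeks 12, 16, 28, 40, 52, F60 |
| Lipids (fasting) | Baseline, Weeks 8, 16, 24, 52, F60 |
| Both | Baseline, Weeks 16, 52, F60 |
| Chemistry only | Screening 2, Weeks 12, 28, 40 |

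SAP Table 5-1 gives the same on-treatment pattern: Group 2 (chemistry) has windows at Weeks 12, 16, 28, 40 and 52, and Group 8 (lipids) at Weeks 8, 16, 24 and 52. F60 can count as on treatment: in Table 8-1 the last dose is on day 336, and 336 + 84 = 420, the F60 day.

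So 3 of 6 scheduled post-baseline glucose draws carry no fasting requirement: 1 of 2 up to Week 16, and 2 of 4 afterwards. If the baseline draw is missing, the baseline falls back to Screening 2, which also has no fasting requirement.

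**Step 2: who is exposed to how many such draws.** Placebo time has one (Week 12). Participants switched from placebo have two on secukinumab (Weeks 28 and 40). Those on secukinumab throughout have three. Let q be the chance that such a draw is graded high when a fasting draw would not be. With k independent draws, the chance of at least one spurious shift is 1 − (1 − q)^k. The documents give no q, so a range is assumed.

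| q | k = 1 | k = 2 | k = 3 |
|---|---|---|---|
| 2% | 2.0% | 4.0% | 5.9% |
| 5% | 5.0% | 9.8% | 14.3% |
| 10% | 10.0% | 19.0% | 27.1% |
| 20% | 20.0% | 36.0% | 48.8% |

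For example, with q = 5% and k = 3: 1 − 0.95³ = 14.3%.

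**Step 3: illustration of size.** Every input here is an assumption:
- upper limit 6.1 mmol/L
- person mean distributed Normal(5.3, SD 0.5)
- fasting draw = person mean + Normal(0, SD 0.33)
- fed draw = person mean + d + Normal(0, SD 0.8), where d is the food effect
- each of the three unrestricted draws is fed with probability f

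The result is P(worst of six draws > 6.1, given baseline ≤ 6.1), by simulation.

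| Case | Share shifting above the limit |
|---|---|
| All six draws fasting (like-for-like reference) | 18% |
| f = 10%, d from 0.25 to 1.0 | 23% to 30% |
| f = 25%, d = 0.25 / 0.5 / 1.0 | 29% / 34% / 45% |
| f = 100%, d = 0.5 / 1.0 | 66% / 86% |

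Two cautions apply. With f = 100% and d = 0, the share is already 42%, so much of the rise comes from the assumed jump in SD from 0.33 to 0.8. Also, Grade 2 starts above 8.9 mmol/L. With all unrestricted draws fed, it is reached by under 0.1% of participants (d = 0.5) or just under 0.5% (d = 1.0), at most about 0.005 × 40 = 0.2 of 40 participants. The protocol's notable limit of 13.9 mmol/L (Table 16-1) is not reached.

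**The case against.** The strongest reply is that comparisons between groups are protected. Both arms follow the same schedule to Week 16. At Week 16 each group is re-randomised between 150 mg and a second regimen whose details are redacted (SAP 1.1), and the final analysis reports four treatment sequences (SAP 2.1.1.1). This stands. A reader might infer that after Week 16 the within-arm shift is the only available reading because placebo has ended. The documents do not support that, since a randomised comparison between regimens remains within each original group.

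A reader might also infer that every column is biased upward. That goes too far. Protocol 8.4.1 leaves sample collection to a laboratory manual that is not among the documents and could require fasting for chemistry. That glucose is fasting at the four shared visits is itself inferred from the shared visit. The artefact arises only if participants eat.

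The by-visit summaries and full listings would partly reveal a rise confined to Weeks 12, 28 and 40, and SAP 2.7 plans no formal safety testing. The Week 16 safety tables were produced earlier under a separate plan. These points lower the importance. They do not remove the mismatch in the worst-value and maximum-change tables, which do not show which visit supplied the value or whether the participant had fasted.

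**Conclusion.** The point holds as a possible inflation, not a demonstrated one. As written, SAP 2.7.3 compares a baseline from a fasting visit with a worst value and a maximum change that can come from three draws with no fasting rule and no flag.

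The randomised comparisons, against placebo to Week 16 and between regimens afterwards, are not biased by this alone. Within-sequence shifts can be. So can the entire-study display of placebo against any secukinumab that SAP 2.1.1.1 allows for some safety summaries, because placebo time has one unrestricted draw and active treatment has two or three. That imbalance comes on top of longer follow-up on active drug.

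The size depends on how many participants eat beforehand, which the documents do not say. The 23–45% range assumes that 10–25% of the unrestricted draws are fed. The 66–86% figures need all of them to be fed and should not be read as expected values. Against the 18% reference, the excess would be almost entirely Grade 1. The point is minor: it affects how descriptive safety tables are read and leaves the efficacy conclusions untouched.

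**What to change.** In SAP 2.7.3, keep the glucose tables that use all values, and flag Weeks 12, 28 and 40 as visits where fasting was not required. Add a CTCAE shift table and a maximum-change table for glucose restricted to baseline, Weeks 16 and 52 and F60. Keeping the full tables matters: dropping the unflagged visits would leave no graded glucose between Weeks 16 and 52, and a genuine high value at Week 28 or 40 would be lost from them.

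The cost is a short SAP addition and some extra output with fewer values per participant. The restricted table should carry a note that three draws give fewer shifts than six even when all are fasting (12% against 18% under the assumptions above), so the gap between the two tables is not all due to food.

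If the laboratory manual already requires fasting for chemistry, one SAP line saying so closes the point. For draws still to come, footnote 13 of Table 8-1 could be extended to the blood chemistry row. That costs a protocol amendment and up to three more fasting visits per participant, and it cannot change samples already taken.
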